11.3. Classification of Adverse Events

Each AE whether serious or non-serious will be classified by the Investigator according to the following rules and definitions.

11.3.1. Relationship to Investigational Product

For each AE, the Investigator determines whether there is a reasonable likelihood that the AE may have been caused by the study treatment according to the categories below:

Unrelated: The event is clearly not related to the IP

Possibly/probably related: The event could be related/is likely to be related to the IP

Definitely related: The event is clearly related to the IP

AEs that the Investigator or Sponsor considers to be possibly, probably, or definitely related to the IP will be considered adverse drug reactions.

11.3.2. Relationship to Study Procedures

For each AE the Investigator determines whether there is a reasonable possibility that the AE may have been caused by the study procedures according to the categories below:

Unrelated: The event is clearly not related to the study procedures

Possibly/probably related: The event could be related/is likely to be related to study

procedures

Definitely related: The event is clearly related to the study procedures

11.3.3. Relationship to Underlying Disease

For each AE the Investigator determines whether there is a reasonable possibility that the AE may be related to the underlying disease according to the categories below:

Unrelated: The event is clearly not related to the underlying disease

Possibly/probably related: The event could be related/is likely to be related to the

underlying disease

Definitely related: The event is clearly related to the underlying disease

Events of disease progression may be considered AEs, based on the investigator's discretion.

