9.6. Blinding and Randomization

This is an open-label study, and therefore patients and Investigators will be aware of the patient's treatment. However, to minimize assessment bias, every effort will be made to keep the clinical evaluators unaware of the treatment group of the patients, and all biological efficacy endpoint evaluations will be performed by blinded assessors.

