11.2. Definition of Adverse Events

11.2.1. Adverse Event (AE)

An AE is any untoward medical occurrence in a clinical trial participant, which does not necessarily have a causal relationship with the investigational drug. An AE can, therefore, be any unfavorable and unintended symptom, sign, disease, condition, or test abnormality that occurs during or after administration of an IP whether or not considered related to the IP. Adverse events include:

- Symptoms described by the patient or signs observed by the Investigator or medical staff.
- Test abnormalities (laboratory tests, ECG, X-rays, etc.) that result in an alteration in medical care (diagnostic or therapeutic).

Abnormalities present at Baseline are considered AEs only if they reoccur after resolution or worsen during the AE collection period.

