11.2.2. Serious Adverse Event (SAE)

An SAE is defined as any AE that results in any of the following:

- **Death**: The patient died as the result of the event.
- Life-threatening event: Any AE that places the patient, in the view of the Investigator or Sponsor, at immediate risk of death from the AE as it occurred, i.e., does not include an AE that had it occurred in a more severe form, might have caused death.

- Required or prolonged inpatient hospitalization: The AE resulted in hospitalization or prolonged an existing hospitalization. Since hospitalization may be part of the study, only hospitalizations that are longer than expected based on Investigator judgment, will be considered prolonged hospitalizations.
- **Persistent or significant disability/incapacity**: An AE that results in a substantial disruption of a person's ability to conduct normal life functions.
- **Congenital anomaly/birth defect**: A congenital anomaly/birth defect that occurs in the offspring of a patient exposed to the IP.
- **Important medical events**: An AE that may not result in death, be life-threatening, or require hospitalization may be considered an SAE when, based upon appropriate medical judgment, the event may jeopardize the patient and may require medical or surgical intervention to prevent one of the outcomes listed above.

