7.9.1 Adverse Events

Adverse events will be coded using Medical Dictionary for Regulatory Activities (MedDRA Version 17.1 or higher). This coding system provides five levels to classify AEs. In general, AEs will be presented by system organ class (SOC) and PT but other classifications may be used if warranted.

The sorting order for the AE incidence tables, unless otherwise specified, will be by decreasing frequency in the active treatment arm. Multiple occurrences of the same AE (at the PT level) in the same patient will be counted only once in the frequency tables. If a patient experiences multiple episodes of the same event with different relationship/severity, the event with the strongest relationship or maximum severity to investigational drug product will be used to summarize AEs by relationship and severity. For example, for the table of AEs by SOC and PTs sorted by decreasing frequency presented by treatment group, SOC will be presented in decreasing frequency order of the active treatment column, and within each SOC, PTs will be presented in decreasing order of active treatment column. A patient is counted only once within each SOC and PT.

If a patient experiences multiple events that map to a single PT, the maximal severity grade and strongest investigator assessment of relation to study medication will be assigned to the PT for the appropriate summaries. Should an event have a missing severity or relationship, it will be classified as having a severity of “SEVERE” and/or a “DEFINITELY RELATED” relationship to study medication.

An overall summary of AEs table will be presented which will include:

- Number of Treatment-emergent AEs (TEAEs)
- Number of TEAEs by Severity
- Number of patients with at least 1 TEAE
- Number of patients with at least 1 Severe TEAE
- Number of patients with at least 1 treatment-related TEAE
- Number of patients with at least 1 treatment-emergent SAE
- Number of patients with at least 1 treatment-related, treatment-emergent SAE
- Number of patients with at least 1 TEAE leading to discontinuation of study drug
- Number of patients with a TEAE leading to death

Treatment-Emergent AEs (TEAEs)

The following TEAEs summary tables will be presented by treatment group:

- TEAEs by SOC and PT
- TEAEs by SOC, PT, and severity

- TEAEs by descending frequency of PT
- Treatment-related TEAEs by SOC and PT
- Treatment-related TEAEs by SOC, PT, and severity
- Treatment-related TEAEs by descending frequency of PT

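### Investigators who know the arm decide case by case whether disease progression is an adverse event, in conflict with the protocol's own AE definition, so by-arm AE and SAE tables partly reflect recording habit

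*Protocol*

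**What the plan says.** Protocol 11.3.3, on relationship to underlying disease, ends with: "Events of disease progression may be considered AEs, based on the investigator's discretion". It gives no criteria and does not list the events it has in mind.

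Protocol 9.6 states: "This is an open-label study, and therefore patients and Investigators will be aware of the patient's treatment". Blinding is sought for other people: "every effort will be made to keep the clinical evaluators unaware of the treatment group of the patients", together with the assessors of biological endpoints. Under 11.6.3 the investigator records AEs and judges their seriousness.

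Protocol 11.2.1 opens with: "An AE is any untoward medical occurrence in a clinical trial participant". It makes no exception for progression, and it treats an abnormality present at baseline as an AE when it worsens during the collection period.

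Protocol 11.2.2 builds the SAE on the AE: an SAE is an AE with one of the listed outcomes. The disability criterion reads: "An AE that results in a substantial disruption of a person's ability to conduct normal life functions". Under 11.5, SAEs must be reported within 24 hours.

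AEs are tabulated by treatment group (Protocol 13.10.2.1; SAP 7.9.1). The SAP's overall summary includes "Number of patients with at least 1 treatment-emergent SAE". SAP 7.9.1 also plans a table of TEAEs that occur in at least 2% of the active group and more often there than in the untreated group.

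**The concern.** Progression is expected in this population. Protocol 5.1 has most boys losing the ability to rise by age 8 and the ability to walk between 10 and 14. Eligible boys are 7 to 16, and Protocol 7.4.1 calls the 300 to 450 m group the one most likely to decline. Whether such a decline enters the AE database is left to individual judgement at about 35 sites, by people who know the arm.

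An investigator might record progression less readily in a treated boy because benefit is expected, or more readily because the drug is under observation. Either habit could produce a difference between arms, or hide one, with no difference in what happened to the boys. The side-by-side tables are the only safety comparison of the arms within the trial, so the events that feed them need a single definition.

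**Working it through.** The documents state no figure that depends on this rule, so there is nothing to reproduce. The check sets the passages side by side and then tests one planned table.

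**1. Two sections give different answers for one event.** Take a boy whose weakness, present at baseline, worsens. Under 11.2.1 this is an untoward occurrence and a baseline abnormality that has worsened, so it falls within the AE definition. Under 11.3.3 recording it is optional. The baseline sentence in 11.2.1 is worded as a restriction, but it plainly leaves worsened abnormalities inside the definition. Two sites could take opposite courses and each cite the protocol.

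**2. The choice carries through to SAEs.** A progression event not recorded as an AE cannot be an SAE under 11.2.2 and does not trigger reporting under 11.5. If it is recorded and meets the disability criterion, it does both. The exception is death: 11.6.2 makes every cause of death an SAE.

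**3. The visible SAP adds no common rule.** It has no list of progression terms, no review of progression events without knowledge of arm, and no table with and without them. Its only medical review of AEs concerns infusion-related reactions.

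**4. Sensitivity of the 2% table.** Planned numbers (Protocol synopsis): treated 70 + 10 = 80; control 20 + 10 = 30; total 110, as stated. The comparison with the untreated group is assumed to use percentages.
- One treated boy: 1/80 = 1.25%, below 2%, not listed.
- Two treated boys, no controls: 2/80 = 2.5% against 0%, listed.
- Two treated boys, one control: 2.5% against 1/30 = 3.3%, not listed.
- Three treated boys, one control: 3/80 = 3.75% against 3.3%, listed again.

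One discretionary entry in either arm can decide whether a term appears. SAP 8.1 expects very few controls. With fewer than 30, one control entry weighs more than 3.3%.

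**5. General form, on assumed inputs.** Let p be the true share of boys with a progression event, equal in both arms, and r the share recorded as an AE. The recorded difference is p × (r treated − r control). The documents give neither p nor r.

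| p | r treated / r control | recorded, treated vs control | difference |
|---|---|---|---|
| 20% | 50% / 50% | 10% vs 10% | 0 |
| 20% | 75% / 25% | 15% vs 5% | +10 points |
| 20% | 25% / 75% | 5% vs 15% | −10 points |
| 40% | 75% / 25% | 30% vs 10% | +20 points |

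This shows the mechanism and is not a forecast. It concerns AEs. The effect on SAEs is smaller to the extent that recorded events fail a seriousness criterion.

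**The case against.** **The progression milestones are not lost.** This stands. Loss of ambulation and loss of rise are assessed in both arms through scheduled 6MWT and NSAA, derived by rule, with site queries on permanent non-ambulation (SAP 6.7), and reported by arm (SAP 7.8.2). A reader might infer that unrecorded events are beyond repair. For these two milestones the documents show otherwise: AE records can be checked against endpoint data. What varies is their AE and SAE status.

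**No test is distorted.** This also stands. Safety analyses are descriptive (Protocol 13.10.2; SAP 7.9), and SAP 8.1 drops inferential comparison of the arms. The effect is on how tables read.

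**AE counts are unequal anyway.** True. AEs are assessed at every visit (Protocol 10.2). Treated boys have weekly infusions and may continue into an extension, while controls have few visits and end at Week 96. Only treated boys have biopsies. This limits what the remedy can achieve, but it does not justify a second, avoidable source of imbalance.

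**Recorded progression can be identified.** Partly true. Each recorded AE carries a judgement of relationship to the underlying disease, which helps to find recorded events. It says nothing about events left unrecorded.

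**Conclusion.** The point holds as a conflict between two protocol sections that affects how the safety tables read. Section 11.3.3 makes recording of non-fatal progression optional for investigators who know the arm, Section 11.2.1 does not, and the choice passes into SAE counts. On the planned 80 and 30, one entry can decide whether a term is listed in the SAP's treated-exceeds-untreated table. Beyond that, direction and size are unknown.

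Two stronger readings are tempting. A reader might infer that discretion moves an arm's SAE percentage by the whole progression rate. That would need all-or-none recording in an arm and every event classed as serious. Loss of rising from the floor does not automatically meet the disability criterion, and the documents give no rate for these events. A reader might also infer that investigators will favour the treated arm. The documents show that recording can differ, not that it will, or which way.

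The change is worth making because it is specific and cheap, but it does not threaten the trial's main conclusions.

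**What to change.** **Protocol.** Reconcile 11.3.3 with 11.2.1 in one written rule for both arms. It should say which progression events are recorded as AEs and which only through the endpoint assessments. It should keep reporting of any worsening suspected to be related to study drug or study procedures, and state how progression that meets a seriousness criterion is reported. A flat instruction never to record progression as an AE would not do: it would contradict 11.2.1 and could remove a safety signal.

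**SAP.** Before lock, and without reference to arm, fix a list of progression preferred terms. Print the TEAE and SAE tables, including the 2% table, with and without those terms. Reconcile AE records against the loss-of-ambulation and loss-of-rise data, and report by arm how many boys with each endpoint event also have a matching AE.

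**Cost.** A short protocol change with a note to sites, one repeated set of AE tables and one reconciliation listing. The protocol change helps only data still to be collected; the SAP part remains possible until final lock. Progression that was neither recorded as an AE nor measured as an endpoint cannot be recovered, and the differences in visit frequency and follow-up remain.

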11.3.4. Severity of Adverse Events

Note that severity is not the same as "seriousness," which is defined in Section 11.2.2 and which serves as a guide for defining regulatory reporting obligations.

The Investigator will assess the severity of all AEs as Mild, Moderate, or Severe, based on the following definitions:

Mild: The event does not interfere with the patient's usual activities.

Moderate: The event interferes with the patient's usual activities.

Severe: The event prevents the patient from undertaking their usual activities

and requires therapeutic intervention or cessation of the IP.

11.3.5. **Outcome**

Outcome describes the status of the AE. The Investigator will provide information regarding the patient outcome of each AE.

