11.3.6. Action Taken Regarding the Investigational Drug Product

The Investigator will provide information regarding the action taken with respect to the IP in response to the AE.

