11.4. Recording Adverse Events

All AEs/SAEs experienced from the time of informed consent/assent to the last follow-up will be recorded within each patient's CRF. Information should include: a concise description of the event; date and time of event onset and resolution; determination of seriousness, severity, corrective treatment, outcome, and relationship to IP or study procedure or underlying disease; and any action taken will be recorded. Resolution occurs when the patient has returned to his Baseline state of health or further improvement or worsening of the event is not expected.

Whenever possible, a diagnosis will be recorded as an AE, rather than symptoms or isolated laboratory abnormalities related to that diagnosis. Several symptoms or laboratory results that are related to the same diagnosis can thus be part of the same AE. A medical or surgical procedure is not an AE; rather the condition leading to the procedure should be recorded as the AE. Similarly, death is not an AE, but is rather the outcome of the AE(s) that resulted in death. If the AE(s) leading to death are not known, then death must be reported as an AE. All AEs will be followed until the resolution of AE, completion of the patient's study participation, or study termination, whichever occurs first. SAEs will be followed until resolution or until the condition stabilizes or returns to Baseline status.

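### The Severe grade adds a treatment-or-stopping condition to function, so some incapacitating adverse events are graded Moderate and the criterion differs slightly between arms

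*Protocol*

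**What the plan says.** Protocol 11.3.4 sets one three-grade scale for both arms: "The Investigator will assess the severity of all AEs as Mild, Moderate, or Severe, based on the following definitions". Mild means no interference with usual activities. Moderate reads "The event interferes with the patient's usual activities". Severe has two parts: "The event prevents the patient from undertaking their usual activities", continued by "and requires therapeutic intervention or cessation of the IP".

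Two nearby sections collect the same facts separately. Protocol 11.3.6 states "The Investigator will provide information regarding the action taken with respect to the IP in response to the AE". Protocol 11.4 lists, for each event, "determination of seriousness, severity, corrective treatment, outcome, and relationship to IP or study procedure or underlying disease".

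The control group receives no eteplirsen (Protocol synopsis and 9.3). Its adverse events are nevertheless summarised in the same way as the treatment-emergent events of treated boys (Protocol 13.10.2.1). SAP 7.9.1 tabulates events by severity and treatment group and includes "Number of patients with at least 1 Severe TEAE" in its overall summary. The SAP gives no severity definition of its own. It only sets a missing severity to Severe (SAP 6.2.4 and 7.9.1).

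**The concern.** The first two grades ask one question: how far does the event limit the boy? The third grade asks that question and also how the event had to be managed. This has two consequences.

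First, an event that stops all usual activities but needs no therapy and no stopping of the drug does not meet Severe. It shares the Moderate grade with events that limit activities only in part. An infusion-related reaction, which is an event of special interest in SAP 7.9.1, could be of this kind.

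Second, one of the two alternatives in the added condition refers to the study drug, which only one arm receives.

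The outputs at stake are the tables by severity (all and treatment-related events), the number of patients with a severe event, and the separate severe counts for events of special interest and the additional events for review. A reader of those tables will take Severe to mean incapacitating and to mean the same thing in both columns.

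**Working it through.** The documents attach no figure to the severity definition, so there is nothing to reproduce. The check is one of logic.

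Let A = the event stops usual activities, B = it requires therapeutic intervention, C = it requires cessation of the study drug.

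- Read naturally, Severe = A and (B or C).
- Treated boys can therefore qualify by A and B, or by A and C.
- In controls C cannot occur, so Severe reduces to A and B.

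| A | B | C | Treated | Control |
|---|---|---|---|---|
| yes | yes | either | Severe | Severe (C cannot occur) |
| yes | no | yes | Severe | pattern cannot occur; the same event without C is Moderate |
| yes | no | no | Moderate | Moderate |

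The third row is the under-grading, and it applies to both arms. The second row is the difference between arms, and it covers a narrow class: incapacitating, no therapy needed, but the drug has to be stopped.

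The sentence could also be parsed as (A and B) or C. That is less natural, and controls would still lack route C.

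Direction, compared with Severe = A alone: both arms lose the third-row events. Controls also lose events that would have fallen in the second row had there been a drug to stop. The result is fewer Severe events overall and relatively more in the treated arm.

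Scale: planned enrolment is about 70 + 10 = 80 treated and 20 + 10 = 30 control boys (Protocol synopsis). One boy moved between grades shifts the proportion with a severe event by 1/80 = 1.25 percentage points in the treated arm and 1/30 = 3.3 points in the control arm. How many boys would move is not in the documents. They give neither the frequency of incapacitating events nor the share that require therapy or stopping.

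Outputs that do not depend on the clause: an event satisfying A is at least Moderate whether or not B or C holds. Any output that pools moderate with severe is therefore unchanged. This includes the SAP 7.9.1 table and listing of events of special interest that are related and/or moderate or severe, and the matching output for the additional events for review.

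**The case against.** The strongest reply is that little depends on this.

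- **No comparison is planned.** SAP 8.1 drops every inferential comparison between treated boys and controls, SAP 7.9 makes safety descriptive, and SAP 4.4.2 calls the control group small with a large dropout rate. This stands, and it is the main reason for the low priority. It does not remove the point, because the severity tables are still shown by arm and a descriptive table relies on its categories meaning the same thing in each column.
- **The arm difference is narrow.** Events that force the drug to be stopped are likely to be suspected drug reactions with no control counterpart. Protocol 5.3 reports no withdrawal for an adverse event and no treatment-related discontinuation through 120 weeks in the earlier extension study. This also stands.
- **Nothing is lost.** Affected events stay in the all-event tables as Moderate. Important ones can also appear as serious events, as events leading to discontinuation, or through the action-taken and corrective-treatment items. This is true, but it does not correct the severe counts.
- **A change now mixes two scales.** The interim analysis has been done and the SAP covers the final analysis. This stands and shapes the fix.

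A reader might also infer more than the text supports. The clause does not exclude every incapacitating event that went untreated: it says *requires*, not *receives*, so an event that needed therapy and did not get it still qualifies as Severe. The clause does not make the drug look safer than control, because the asymmetry adds Severe events to the treated arm. No numerical gap between arms can be claimed, because any such figure would rest on rates that appear nowhere in the documents.

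**Conclusion.** The point holds as a defect of definition. Severe in Protocol 11.3.4 is not a pure severity grade. It under-grades incapacitating events that require neither therapy nor stopping the drug, and it offers controls one route fewer. The SAP does not repair this; setting missing severity to Severe acts only on ungraded events.

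The under-grading in both arms is the firmer half, because it affects the treated arm's own safety profile without any comparison. The arm difference is real in logic but probably small in practice. The size of either cannot be estimated from the documents.

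The conclusion assumes that investigators apply the wording literally and that no completion guideline outside these documents overrides it. It does not touch efficacy or the all-event counts. Minor priority.

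**What to change.** **Definition.** In Protocol 11.3.4 and the CRF completion guideline, let Severe read "The event prevents the patient from undertaking their usual activities" and stop there. No information is lost, because corrective treatment and action on the drug already have their own items (Protocol 11.3.6 and 11.4).

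**Events already graded.** Keep the grade as recorded. Footnote the definition in the severity tables, and add a combined moderate-or-severe row to the by-arm severity tables. That row is the same under either definition. It does not recover the incapacitating events now held under Moderate; it only gives a line that reads the same way in both arms.

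**Cost.** One line of protocol and guideline text, one table row and one footnote. Slightly more events will be graded Severe. A further footnote is needed wherever grades under the current and revised definitions are mixed within this study or pooled with other studies. If no further events are to be graded, only the footnote and the added row apply.
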